8.1.8. Analysis of Adverse Events by Treatment Sequence (Final Analysis only)

For the final analysis (when all long-term data is available), an additional “as-treated” analysis of All TEAEs, SAEs, and AEs will be provided. The number and percentage of subjects with events will be displayed by overall treatment group and for each of the treatment sequences within a treatment group as shown below:

For placebo group,

All Placebo	DB Placebo E/T Prior to Week 26*	Placebo exposure: DB Placebo to OL Filgotinib	DB Placebo at/after Week 26*
-------------	--	---	------------------------------------

For filgotinib group,

All Filgotinib	DB Filgotinib E/T Prior to Week 26*	Filgotinib exposure: DB Placebo to OL Filgotinib	DB Filgotinib to OL Filgotinib	DB Filgotinib at/after Week 26*
----------------	---	--	--------------------------------------	---------------------------------------

DB = double-blind; E/T = early termination of study drug; OL = open-label; * = subject never received OL filgotinib (either met perm stopping criteria and entered monitoring phase or E/T for other reasons).

8.2. Laboratory Evaluations

Laboratory data collected during the study will be summarized using both quantitative and qualitative methods. Summaries of laboratory data will be provided for the Safety Analysis Set and will be by actual treatment using an “as-treated” analysis. For “as-treated” displays, subjects on double-blind placebo who switch to open-label filgotinib will have data collected up to first dose date of filgotinib attributed to placebo (summarized with placebo) and data collected after first dose of open-label filgotinib to last dose date of filgotinib + 30 days attributed to filgotinib (summarized with filgotinib). Other subjects will have post-baseline data included up to last dose date + 30 days if terminated from study drug; or all available data at time of an interim analysis.

Analysis will be based on values reported in conventional units. When values are below the LOQ, they will be listed as such, and the closest imputed value will be used for the purpose of calculating summary statistics as specified in Section 3.7. Hemolyzed test results will not be included in the analysis, but they will be listed in by-subject laboratory listings.

A by-subject listing for laboratory test results will be provided by subject ID number and time point in chronological order for hematology, serum chemistry, and urinalysis separately. Values falling outside of the relevant reference range and/or having a severity grade of 1 or higher based on CTCAE criteria will be flagged in the data listings, as appropriate.

No formal statistical testing is planned.

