8.5.7. Laboratory Evaluations

Selected laboratory data will be summarized (n, mean, SD, median, Q1, Q3, minimum, and maximum) by treatment group and Study Visit along with corresponding change from Baseline. The incidence of treatment-emergent graded laboratory abnormalities will be summarized similarly.

Graded laboratory abnormalities will be defined using CTCAE 4.03 grading scale in [Appendix 4](#).

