- Subjects with a decrease of $\geq 50\%$ in sperm concentration and/or motility and/or morphology from baseline will have study drug stopped and an investigator selected standard of care treatment that is in accordance with the protocol started. Semen samples will be collected off study drug treatment every 13 weeks during the Monitoring Phase until reversibility is met or for up to 52 weeks, whichever occurs first. Reversibility is met when all sperm parameter(s) qualifying the subject to enter the Monitoring Phase return to greater than 50% of the baseline value (ie, greater than $0.5 \times$ [mean of 2 evaluable samples collected at the screening visit]). Data will be summarized for each sperm parameter meeting a pre-specified sperm decrease threshold at the visit when study drug was stopped. The number (percent) who met reversibility criteria and the cumulative number (percent) who met reversibility criteria at each Monitoring Phase visit will be presented separately for subjects who met pre-specified sperm decreases at Week 13 (summarized by double-blind treatment group) and for subjects meeting pre-specified sperm parameter decrease thresholds at the Week 26/OL Week 13 analysis visit or at/after Week 39/OL Week 26 and up to last dose date of any study drug + 7 days (summarized by treatment sequence).

The following subject groupings will be applied to safety data according to the actual treatment received (filgotinib or placebo) unless otherwise stated:

- An “as-treated” analysis will be performed for safety data. Subjects who took double-blind placebo and switched to open-label filgotinib will have data reported during the placebo period summarized with the placebo group, and data reported during the open-label filgotinib period summarized with the filgotinib group (baseline will be open-label baseline). Subjects who switch from double-blind filgotinib to open-label filgotinib and subjects who stay on double-blind study drug for the duration of study will be summarized by their double-blind treatment group (baseline will be double-blind baseline).

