Adverse events will additionally be displayed for the double-blind treatment phase (to align with the period summarized for the primary analysis of semen data). Data will be summarized by double-blind treatment group (ie, filgotinib 200 mg or placebo) from first dose date of double-blind study drug up to the first dose date of open-label filgotinib (minus 1 day for AEs) for subjects who switch to open-label filgotinib; to last dose date of double-blind study drug + 30 days for subjects who stop double-blind study drug and do not switch to open-label filgotinib; or all available data at time of interim analysis (for subjects ongoing on double-blind treatment at the time of an interim analysis).

Select AE summaries (eg, brief summary of AEs while on open-label filgotinib, AEs leading to interruption of open-label filgotinib, and AEs leading to discontinuation of open-label filgotinib) will be displayed for subjects in the Open-Label Filgotinib Safety Analysis Set. AEs occurring from first to last dose date of open-label filgotinib plus 30 days (for those permanently discontinued from drug) or all events on/after open-label first dose date for those ongoing on open-label filgotinib will be included.

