5. BASELINE CHARACTERISTICS

5.1. Demographics

Subject demographic variables (ie, age, sex, race, and ethnicity) will be summarized for the double-blind phase of the study by treatment group and overall for the ITT/Safety Analysis Sets and the Semen Analysis Set using descriptive statistics for age, and using number and percentage of subjects for sex, race and ethnicity. Separate displays will present data for the “as-treated analysis” by treatment for the Safety Analysis Set and by treatment sequence for the Week 26/ LTE Semen Analysis Set. Subjects who were randomized to placebo and switched to open-label filgotinib will be counted in both the placebo and the filgotinib group for “as-treated” displays.

Age is calculated in years on the date of first study drug administration. If a subject does not receive study drug after randomization, the subject’s age will be calculated from the Day 1/baseline assessment. A by-subject demographic listing, including the informed consent date, will be provided by subject ID number in ascending order.

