8.2.3. Liver-related Laboratory Evaluations

Liver-related abnormalities will be examined and summarized using an “as-treated” analysis of the number and percentage of subjects with at least 1 value in the reporting period for the following:

- AST: (a) > 3 times the upper limit of normal range (ULN); (b) > 5 x ULN; (c) > 10 x ULN; (d) > 20 x ULN
- ALT: (a) > 3 x ULN; (b) > 5 x ULN; (c) > 10 x ULN; (d) > 20 x ULN
- (AST or ALT > 3 x ULN) and (total bilirubin > 2 x ULN)

For individual laboratory tests, subjects will be counted once based on their most severe postbaseline value up to last dose date plus 30 days. For the composite endpoint of AST or ALT and total bilirubin, subjects will be counted once when the criteria are met at the same postbaseline visit date. The denominator is the number of subjects in the Safety Analysis Set who have at least 1 nonmissing postbaseline value of all relevant tests at the same postbaseline visit date. A listing of subjects who met at least 1 of the above criteria will be provided.

For “as-treated” displays and subjects randomized to placebo who switched to open-label filgotinib, the most severe postbaseline value collected up to the first dose date of open-label filgotinib will be summarized with the placebo group. The most severe postbaseline value collected after first dose date and up to the last dose date of open-label filgotinib plus 30 days will be summarized with the filgotinib group.

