8.3. Body Weight and Vital Signs

Descriptive statistics will be provided by treatment using an “as-treated” analysis for body weight, BMI and vital signs (pulse, systolic and diastolic blood pressure, respiration rate, and temperature) as follows:

- Baseline value
- Values at each postbaseline time point
- Change from baseline at each postbaseline time point

A baseline value will be defined as the last available value collected on or prior to the date of first dose of study drug. For “as-treated” displays and subjects who took double-blind placebo and switched to open-label filgotinib, the baseline value will be used to calculate change from baseline during the double-blind placebo period (summarized with placebo group). The Open-Label Baseline will be used to calculate change from baseline for values collected after the first dose date and up to last dose date of open-label filgotinib plus 30 days (summarized with filgotinib group). Change from baseline to a postbaseline visit will be defined as the postbaseline value minus the baseline value.

In the case of multiple values in an analysis window, data will be selected for analysis as described in Section 3.7.3. No formal statistical testing is planned.

A by-subject listing of vital signs will be provided by subject ID number and time point in chronological order. Body weight, height, and BMI will be included in the vital signs listing, if space permits. If not, they will be provided separately.

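### Hematology, chemistry, urinalysis, lipid, liver, weight and vital-sign results are planned only as-treated, so no by-visit row is a purely randomized comparison

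*SAP*

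**What the plan says.** SAP 8.2 sets the rule for hematology, chemistry, urinalysis and lipids: "Summaries of laboratory data will be provided for the Safety Analysis Set and will be by actual treatment using an" as-treated analysis. SAP 8.2.3 repeats it ("Liver-related abnormalities will be examined and summarized using an" as-treated analysis), and so does SAP 8.3 for weight, BMI and vital signs ("Descriptive statistics will be provided by treatment using an" as-treated analysis). Protocol 8.5.7 is less specific: "Selected laboratory data will be summarized (n, mean, SD, median, Q1, Q3, minimum, and maximum) by treatment group and Study Visit".

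Under these rules a placebo man who switches gives his earlier data to placebo, and "data collected after first dose of open-label filgotinib to last dose date of filgotinib + 30 days attributed to filgotinib". SAP 3.2 adds that he has "data reported during the open-label filgotinib period summarized with the filgotinib group (baseline will be open-label baseline"). SAP 3.7.2 restarts his visit clock at the first open-label dose. SAP 5.1 states the consequence for demographics: "Subjects who were randomized to placebo and switched to open-label filgotinib will be counted in both the placebo and the filgotinib group for" as-treated displays. For laboratory and vital-sign data the same follows from the attribution rules.

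Other data are treated differently. SAP 3.2 says: "Adverse events will additionally be displayed for the double-blind treatment phase". Semen and hormone data have as-randomized visit windows (SAP 3.7.2), and LH, FSH, inhibin B and testosterone are compared by double-blind group at Weeks 4 and 13 (SAP 6.6.3). ECG results are shown by treatment sequence (SAP 8.5). The concern does not extend to any of these.

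**The concern.** Up to the Week 13 visit the plan keeps all men on their assigned blinded drug, so those 13 weeks give the cleanest randomized comparison of laboratory and vital-sign changes. No planned table isolates it.

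The open-label visits at Weeks 2, 4, 8 and 13 fall into the filgotinib rows with the same labels. The switchers placed there were selected: they were non-responders at Week 13 or worsened afterwards, and had not met a sperm decrease threshold. They also follow different co-medication rules, because steroid tapering may begin at Week 13 and azathioprine or 6-mercaptopurine doses may be adjusted between Weeks 13 and 26 (Protocol 5.3.1).

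The abnormality tables raise a second issue. They report numbers and percentages of men (SAP 8.2.2.3) without adjusting for time at risk, although exposure-adjusted rates are planned for adverse events of interest (SAP 8.1.7). A switch ends a man's placebo follow-up and starts filgotinib follow-up.

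At stake is how blood counts, lipids and liver tests are read. Protocol 1.4 relies on hematology to monitor a possible effect on lymphocytes and names lipid and hemoglobin changes as potential benefits.

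**Working it through.** **Column sizes.** The plan's own figure comes first. With 100 evaluable men per group and 20% non-evaluable (Protocol 8.7), 100/(1 − 0.20) = 125 per arm, which matches. Let s be the share of placebo men who switch. The documents give no value for s in this trial. The Phase 2 Crohn's disease study quoted in Protocol 1.3.2 had 41% placebo response, so 59% non-response, which is one marker for the upper range.

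The placebo column holds 125 men and the filgotinib column 125 + 125s. The switchers' share of the filgotinib column is s/(1 + s).

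| s (assumed) | Filgotinib column | Switchers' share |
|---|---|---|
| 20% | 150 | 17% |
| 40% | 175 | 29% |
| 59% | 199 | 37% |

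For s = 30%, 50% and 70% the share is 0.3/1.3 = 23%, 0.5/1.5 = 33% and 0.7/1.7 = 41%.

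**By-visit rows.** Set SAP 3.7.2 beside SAP 8.2.1. In the filgotinib rows for Weeks 2 to 13, a man randomized to filgotinib is counted from his first double-blind dose against his double-blind baseline. A switcher is counted from his first open-label dose against his open-label baseline. The placebo rows to Week 13 are unmixed, but the filgotinib rows are not.

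**Crude percentages with no drug effect.** Assume the same constant hazard of 0.2 per year on both treatments, switching at Week 13, and no other dropout. The risk by week w is f(w) = 1 − exp(−0.2w/52), so f(13) = 0.0488, f(26) = 0.0952, f(65) = 0.2212 and f(78) = 0.2592. Take s = 0.4.

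Follow-up to 26 weeks:
- Placebo: 0.6 × 0.0952 + 0.4 × 0.0488 = 7.7%
- Filgotinib: (0.0952 + 0.4 × 0.0488)/1.4 = 8.2%

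Follow-up to 78 weeks:
- Placebo: 0.6 × 0.2592 + 0.4 × 0.0488 = 17.5%
- Filgotinib: (0.2592 + 0.4 × 0.2212)/1.4 = 24.8%

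Other values of s at 78 weeks give 21.7% against 25.3% (s = 20%) and 13.5% against 24.5% (s = 59%). With a hazard of 0.5 per year and s = 40%, the figures are 18.0% against 19.2% at 26 weeks and 36.4% against 51.0% at 78 weeks.

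**Source of the gap.** At 78 weeks with s = 40%, mean placebo follow-up is 0.6 × 78 + 0.4 × 13 = 52 weeks. Mean filgotinib follow-up is (78 + 0.4 × 65)/1.4 = 74 weeks. Men randomized to filgotinib alone would show 25.9%, so including switchers lowers that column to 24.8%. The gap therefore comes from shortened placebo follow-up.

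**The case against.** The strongest reply is that the plan follows Protocol 8.5.4, which summarizes safety data by the study drug received. Safety and tolerability is an exploratory objective, the tables are descriptive with no formal testing, and the by-subject listings would allow anyone to rebuild a double-blind comparison. All of this is true: it is a weakness of the planned tables, with no departure from the protocol and no loss of data. It does not remove the mixing. Side-by-side columns and line plots by treatment group invite a comparison whether or not a test is run, and listings do not replace a table.

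Three stronger readings are tempting, and the documents do not support them.

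- A reader might infer that the randomized period is never used for laboratory safety. The sex hormones are among the tests in Protocol Appendix 6 and are compared by double-blind group. Protocol 7.5 also requires abnormalities that need intervention, or that lead to drug interruption or discontinuation, to be recorded as adverse events, which have a double-blind display. Part A data for the other tests are included in the tables, but not isolated. Blinded drug also continues beyond Part A, in Part B and for some men in the extension.
- A reader might infer that column differences say nothing about the drug. Switchers are measured from a baseline before filgotinib and by time since first filgotinib dose, so the mixture is aligned on exposure. On the assumed switch rates, 59% to 77% of the filgotinib column was randomized to it. The contrast is diluted and partly confounded, but still carries information.
- A reader might blame the gap in crude percentages on men appearing in both columns. The working shows that including the switchers narrows it.

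**Conclusion.** The concern holds for the tests in SAP 8.2 and for weight, BMI and vital signs in 8.3. Their only planned summaries are as-treated, and no by-visit row is a purely randomized contrast. Switchers would be 23% to 41% of the filgotinib column if 30% to 70% of placebo men switch.

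Unequal follow-up in the abnormality tables matters little early (about half a percentage point at 26 weeks) and more later (about 7 points at 78 weeks), given a hazard of 0.2 per year, 40% switching and no drug effect. Switch rates, hazards and follow-up are all assumptions, so these figures show the mechanism and its order of size; they do not predict the trial's results. The semen and hormone analyses are unaffected. A better comparison is available from data already collected, so the change is worth making.

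**What to change.** Add to SAP 8.2, 8.2.3 and 8.3 a double-blind-phase display by double-blind treatment group, measured from the double-blind baseline. It should cover numeric laboratory tests, graded and marked abnormalities, liver criteria, weight and vital signs. Use the cut the SAP already applies to adverse events: before the first open-label dose for men who switch, and last double-blind dose plus 30 days for those who stop without switching. The cut is needed even at Week 13, because that window runs to Day 116 in SAP Table 3-2 and Day 137 in Table 3-1, so it could take in early open-label results.

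Name the by-visit rows through Week 13 as the main randomized comparison. After Week 13 the double-blind period still ends sooner for men who switch, so show exposure time beside any percentage that covers the whole period. Keep the as-treated tables as long-term descriptive data.

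Also reconcile the analysis sets: SAP 8.2 names the Safety Analysis Set, which SAP 3.1.3 assigns to the double-blind phase, although that section defines a separate As-Treated Safety Analysis Set.

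The cost is SAP wording and a small number of extra tables from existing programs, with no new data. They can be added for the final analysis and recorded in the clinical study report, as SAP Section 1 provides for changes after finalization.

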8.2.1. Summaries of Numeric Laboratory Results

Descriptive statistics will be provided by treatment group for selected laboratory tests as follows:

- Baseline values
- Values at each postbaseline time point
- Change from baseline at each postbaseline time point

A baseline laboratory value will be defined as the last measurement obtained on or prior to the first dose date of double-blind study drug. For “as-treated” displays, subjects who took double-blind placebo and switched to open-label filgotinib will have the baseline value used for placebo period and the Open-label Baseline will be used for the analysis for data collected after the first dose of open-label filgotinib. Data collected while on double-blind placebo will be summarized with placebo treatment, and data collected while on open-label filgotinib will be summarized with filgotinib. Change from baseline to a postbaseline visit will be defined as the visit value minus the baseline value (or minus OL baseline for the filgotinib period for “as-treated” analysis for subjects who switched from double-blind placebo to OL filgotinib). The mean, median, Q1, Q3, minimum, and maximum values will be displayed to the reported number of digits; SD values will be displayed to the reported number of digits plus 1.

Median (Q1, Q3) change from baseline for selected laboratory tests will be plotted using a line plot by treatment group and time point.

In the case of multiple values in an analysis window, data will be selected for analysis as described in Section 3.7.3.

8.2.2. Graded Laboratory Values

The CTCAE version 4.03 will be used to assign toxicity grades (0 to 4) to laboratory results for analysis. Grade 0 includes all values that do not meet the criteria for an abnormality of at least Grade 1. For laboratory tests with criteria for both increased and decreased levels, analyses for each direction (ie, increased, decreased) will be presented separately.

8.2.2.1. Treatment-Emergent Laboratory Abnormalities

Treatment-emergent laboratory abnormalities are defined as values that increase at least 1 toxicity grade from baseline at any postbaseline time point, up to and including the date of last dose of any study drug plus 30 days for subjects who permanently discontinued study drug, or the last available date in the database snapshot for subjects who were still on treatment at the time of an interim analysis.

For “as-treated” displays and subjects who took double-blind placebo and switched to open-label filgotinib, treatment-emergent laboratory abnormalities for the placebo period (summarized with placebo group) are defined as values that increase at least 1 toxicity grade from baseline at any postbaseline time point, up to and including the first dose date of open-label filgotinib. Treatment-emergent laboratory abnormalities of the filgotinib period (summarized with filgotinib group) are defined as values that increase at least 1 toxicity grade from the Open-label Baseline up to and including the date of last dose of any study drug plus 30 days, or the last available date in the database snapshot for subjects who were still on treatment at the time of an interim analysis.

For all other subjects, treatment-emergent laboratory abnormalities are defined as values that increase 1 toxicity grade from the double-blind baseline at any postbaseline time point, up to and including the date of last dose of any study drug plus 30 days (or all available data if ongoing at an interim analysis).

If the relevant baseline laboratory value is missing, any abnormality of at least Grade 1 observed within the time frame specified above will be considered treatment emergent.

8.2.2.2. Treatment-Emergent Marked Laboratory Abnormalities

Treatment-emergent marked laboratory abnormalities are defined as values that increase from baseline by at least 3 toxicity grades at any postbaseline time point, up to and including the date of the last dose of any study drug plus 30 days for subjects who permanently discontinued study drug or the last available date in the database snapshot for subjects who were still on treatment at the time of an interim analysis.

For “as-treated” displays and placebo-treated subjects who switch to open-label filgotinib, treatment-emergent marked laboratory abnormalities of the placebo period (summarized with placebo group) are defined as values that increase at least 3 toxicity grades from baseline at any postbaseline time point, up to and including the first dose date of open-label filgotinib. Treatment-emergent laboratory abnormalities during the open-label filgotinib period (summarized with filgotinib group) are defined as values that increase at least 3 toxicity grades from Open-label Baseline at any postbaseline time point, up to and including the date of last dose of any study drug plus 30 days, or the last available date in the database snapshot for subjects who were still on treatment at the time of an interim analysis.

For all other subjects, treatment-emergent laboratory abnormalities are defined as values that increase 3 toxicity grades from the double-blind baseline at any postbaseline time point, up to and including the date of last dose of any study drug plus 30 days (or all available data if ongoing at an interim analysis).

If the relevant baseline laboratory value is missing, any Grade 3 or 4 values observed within the timeframe specified above will be considered treatment-emergent marked abnormalities.

